Transperineal ultrasound will then be carried out between gestations 24-42 weeks when a vaginal or speculum examination is otherwise also required to assess acceptability and feasibility. This scan will be done either immediately before or after the digital vaginal examination and the timing in relation the digital vaginal examination will be recorded.

Predictive Model:

In the predictive model group, there are no additional questionnaires. An admission ultrasound scan will be performed when the patient is deemed to be in established labour by the attending clinician. Subsequent scans will be performed as required at the time of routine clinical examinations typically between 2-4 hours apart.

The admission ultrasound scan will include if feasible fetal Doppler assessment of the umbilical artery, the cerebro-umbilical ratio (C/U: MCA/PI)¹⁶. Amniotic fluid index will also be measured. Fetal position will be assessed with a transabdominal scan and recorded as described above.

Dataset

Fixed variables

Maternal

Gestation

BMI, Age²⁸, Parity, Height, Ethnicity

Contraindication to vaginal examinations

Reason for avoidance of vaginal examinations

Fetal

EFW if known

Singleton

Multiple

Intrapartum

Non-USS:

Rupture of Membranes Yes/No: If Yes: Time

Spontaneous onset of labour Yes/No: If Yes: Time

Induction of Labour with prostaglandins Yes/No: If Yes: Time at insertion of prostaglandin

Syntocinon Yes/No: If Yes: Time
Epidural analgesia Yes/No: If Yes: Time

Modifiable parameters

USS Parameters: modified as labour progresses

- head position (TA ultrasound scan)
- cervical dilatation
- head-perineum distance
- caput
- moulding

Prolonged first stage of labour will be diagnosed according to national guidelines set in the UK by the National Institute of Health and Clinical Excellence (NICE) guidelines (cervical dilatation of < 2 cm in 4 hours)²⁵.

If recruited to the study, all patients will undergo normal clinical management with digital VEs or speculum examination performed as planned and in addition, ultrasound examinations before the digital VE/speculum by trained professionals. These ultrasound examinations will be blinded to the normal caregivers (midwives or doctors) so that they do not influence clinical management, though for practical reasons it will not be possible to blind the ultrasound operator to the clinical findings.

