A recent study by our group has shown that 95%¹⁵ of transperineal ultrasound parameters can be obtained compared to 82% of digital vaginal examination parameters¹⁵. With an alpha of 0.05 and a power of 90%, the minimum sample size required is 250 patients.

Labour prediction model

For the labour prediction model, there are approximately 15 variables with 10 patients needed per variable³²⁻³⁴ and an approximate 25% Caesarean section rate^{28,35,36} (the primary outcome) in the UK currently. This equates to 600 patients needed for the study.

Calculation:

$$15 \times 10 \times (100/25) = 600 \text{ patients}$$

As already discussed above, for statistical power and significance, a minimum of 42 and 250 patients is required for acceptability and feasibility respectively (24-42 weeks). For the predictive modelling, 600 patients are required (37-42 weeks).

The majority of the patients for the acceptability and feasibility samples will be recruited from the predictive modelling group (gestation 37-42 weeks). However, to allow sufficient data collection for feasibility, acceptability and development of the model, at least 700 patients will be required. As the trust has an annual delivery rate of 9000 annually, over a 24-month data collection period with a delivery rate of 18,000 across the trust, 700 patients (4%) sample size is achievable.

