7.1 Statistical and Data Analysis

In both groups, data will be collected prospectively and compared with vaginal examinations. In the second group, there will also be additional longitudinal measurements.

We will use a p value of <0.05 to indicate significance.

All measurements will be entered online at the time of examination to a secure database on the Imperial College Healthcare NHS Trust shared server where the patient will be identified by study number only. The database entry page will be accessible to investigators on their login, though they cannot interrogate data already entered. The data rules will follow closely to those performed through the recently completed multicentre European TRUFFLE study of fetal growth restriction where ultrasound measurements were captured at the time of examination³⁷.

For 24-42 weeks assessment of acceptability and feasibility:

Acceptability and preference will be tested using a questionnaire with Likert scale for discomfort, adapted from the W-DEQ Score³⁸

Feasibility of the ultrasound technique will be compared to digital VE for (a) total number of observations missing (head descent, position and cervical dilatation) during an admission on the delivery unit and (b) number of ultrasound examinations or digital VEs that could not be carried out for whatever reason where there was an intention to carry out a digital VE.

As a part of feasibility, *Reproducibility* between the *ultrasound and digital VE techniques* will be assessed both as a correlation (r) and agreement (using the Bland Altman method) between the ultrasound method and digital VE for head descent and cervical dilatation, and the Kappa statistic for head position.

Term predictive model:

The predictive value of intrapartum ultrasound parameters will be investigated using linear and logistic regression analyses. We will calculate the Receiver Operating Characteristic (ROC) curve with the Area Under the Curve (AUC) and associated positive and negative predictive values for delivery outcomes in the evaluation of transperineal ultrasound as a diagnostic tool.

8. Study supervision and Monitoring

Central and local supervision: the chief principal investigator at Imperial College London will be responsible for the protocol, quality control, interim analyses of the data, advice on progress and final analysis and reporting of the study. The Imperial Joint Research Compliance Office may audit the study as part of routine research governance.

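### The 600-woman model sample makes no allowance for missing predictors; complete-case regression would leave about 8.1 to 9.5 events per variable on scan parameters alone, not 10

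*Combined protocol and SAP*

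**What the plan says.** Section 7 (Labour prediction model) states that "there are approximately 15 variables with 10 patients needed per variable", takes an "approximate 25% Caesarean section rate", and concludes: "This equates to 600 patients needed for the study". The calculation shown there has three terms: variables, patients per variable and event rate.

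The feasibility paragraph just before it reports that an earlier study by the group "has shown that 95%¹⁵ of transperineal ultrasound parameters can be obtained", and uses that figure to reach its own sample size of 250.

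Section 4.9 describes what is collected for the model:

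- Five repeated scan measurements appear under the label "USS Parameters: modified as labour progresses": head position (transabdominal), cervical dilatation, head-perineum distance, caput and moulding.
- Estimated fetal weight is recorded only where it is known.
- Doppler is conditional: "The admission ultrasound scan will include if feasible fetal Doppler assessment of the umbilical artery".

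Section 7.1 says that the predictive value of the ultrasound parameters "will be investigated using linear and logistic regression analyses". It counts missing observations as a feasibility outcome. It does not say how a woman with a missing predictor is handled in the model.

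On the overall target, section 7 says that "to allow sufficient data collection for feasibility, acceptability and development of the model, at least 700 patients will be required".

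**The concern.** One planning paragraph accepts that some scan parameters will not be obtained; the next sizes a model on those parameters as if all of them were. The 600 leaves no slack: all 150 expected events must have complete predictors for the rule of 10 per variable to be met.

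Ordinary linear or logistic regression software omits any record with a missing predictor unless told otherwise. Without a stated method, the model would by default be fitted to fewer women and fewer events than section 7 claims. There is also a question of who is lost. If the chance that a measurement is missing depends on how the labour or the examination is going, the women left in the model could differ from the nulliparous labouring women it is meant for.

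The model is a primary objective. If nothing is prespecified, the choice between dropping women, dropping predictors and imputing will be made after the data have been seen.

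**Working it through.** **Inputs from the documents.** Section 7: about 15 variables, 10 events per variable, 25% event rate, 95% of transperineal parameters obtained, 82% of digital examination parameters obtained, overall target at least 700. Sections 4.9 and 5.1: four of the scan parameters are transperineal (cervical dilatation, head-perineum distance, caput, moulding); head position is transabdominal.

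**1. The plan's figure.** 15 × 10 × (100/25) = 600, which matches. Expected events: 600 × 0.25 = 150; per variable: 150/15 = 10. There is no term for incomplete predictors.

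**2. Is 95% a working assumption of the plan?** Comparing 0.95 with 0.82, two-sided alpha 0.05, power 90%, pooled variance under the null (mean proportion 0.885), no continuity correction:

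n per group = [1.960 × √(2 × 0.885 × 0.115) + 1.282 × √(0.95 × 0.05 + 0.82 × 0.18)]² / 0.13² = (0.884 + 0.566)² / 0.0169 ≈ 124.5, so 125 per group and 250 in total.

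This reproduces the stated 250, so the 95% is used for planning and is not just background.

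**3. Complete cases on the four transperineal parameters.** Let f be the share of women with all four. Then complete women = 600f, events = 150f and events per variable = 10f. Assumptions: a model using one scan per woman, 95% applying to each parameter, and every other predictor complete.

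| How the gaps fall | f | Women | Events | Events per variable | Recruits for 600 complete (600/f) |
|---|---|---|---|---|---|
| Same women miss all four | 0.95 | 570 | 142.5 | 9.5 | 632 |
| Independent | 0.95⁴ = 0.8145 | 489 | 122 | 8.1 | 737 |

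If no woman missed more than one parameter, f = 1 − 4 × 0.05 = 0.80, giving 480 women and 8.0 per variable, barely below the independent case.

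**4. Fetal weight and Doppler.** The documents give no availability for either. As an illustration only, suppose both are required, each is available in the same assumed share of women, and both are independent of everything else:

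- 95% each (factor 0.9025): f = 0.735 to 0.857, or 7.4 to 8.6 per variable.
- 80% each (factor 0.64): f = 0.521 to 0.608, or 5.2 to 6.1 per variable.

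**5. Does the 700 cover it?** It would give 600 complete cases only if 600/700 = 85.7% of women were complete and all 700 were eligible for the model. Under independence, 700 × 0.8145 = 570 women, 142.5 events and 9.5 per variable. With full overlap, 700 × 0.95 = 665 women and 11.1 per variable.

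**The case against.** The strongest reply is that the loss is modest and uncertain. The protocol never prescribes complete-case analysis. Its inputs are described as approximate. The 95% is a pooled figure from an earlier study, not a rate per woman or per parameter. Repeat scans, typically 2 to 4 hours apart, may recover a value missed once. There is also a target of at least 700. All of this is fair, and it limits the size of the point. It does not supply a missing-data rule. Nor is the 700 an allowance for missing predictors: section 7 shares it with feasibility and acceptability, and it may include multiparous women, multiple pregnancies and women not in established labour, all of whom section 4.5 excludes from the model.

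A reader might infer more than the documents support in three ways:

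- **All five scan parameters at 95%.** This would give 600 × 0.95⁵ = 464 women and 7.7 per variable. Head position is transabdominal, however, and the 95% refers to transperineal parameters.
- **A collapse in events because fetal weight is often unknown.** The 15 variables are not named, so fetal weight is not shown to be a required predictor, and no availability rate is given. The same holds for Doppler, although section 2.1 suggests that it may inform a model for presumed fetal distress.
- **A model that describes only women with a growth scan and an easy examination.** The documents do not say when fetal weight is known or why scans fail. Selection is a possibility, not a demonstrated consequence.

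**Conclusion.** The point holds in a limited form. The 600 meets the plan's own 10 events per variable only if predictors are complete, and the plan elsewhere expects that they will not all be. Left to the software default, the model would have about 489 to 570 women, 122 to 143 events and 8.1 to 9.5 events per variable on the scan parameters alone. This rests on 95% completeness for each of four transperineal parameters, a single-scan model, no other missing predictors, and gaps ranging from independent to fully overlapping. Any further loss from fetal weight or Doppler cannot be sized from the documents. The shortfall does not invalidate the model, but the handling of missing predictors should be settled before analysis.

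**What to change.** **Section 7.1:** state that the term model will be fitted with multiple imputation of missing predictors, with an imputation model that includes the outcome and all predictors, and that a complete-case analysis will be reported as a sensitivity check.

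**Section 7:** state that 10 events per variable holds only with complete or imputed predictors, and that a complete-case analysis of 600 women would give about 8.1 to 9.5 per variable for the scan parameters alone.

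This needs no additional patients. Doppler need not be moved out of the main model to achieve it; doing so would sit badly with the rationale in section 2.1. The costs are some analysis work, reliance on a missing-at-random assumption that the data cannot confirm, and a slightly less favourable stated figure.

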4.10 Study Closure

Data will be collected over the 24 months data collection period.

4.11 Documentation

Recruitment of patients will be noted in the NHS notes. Where photographs of the ultrasound images were obtained, these will be saved securely onto an NHS computer and/or printed in hard copy, which will be filed in a locked secure area. Data will be stored for a minimum of 10 years after completion of study, including the follow up period.

4.12 Patient Engagement

Patients were involved in the creation of the initial study¹⁵ through the Cambridge Maternity Services Liaison Committee, and their feedback from the participation helped shape this research proposal. We have received outline support for the project from the RCOG Intrapartum Care Clinical Study Group led by [name] in 2012 and lay representatives, though this latest iteration of the project design has not yet been submitted to the group. Patient views are important in designing this study to maximise recruitment and we have previously consulted the RCOG to invite lay members to steering committees of a similar previous study (Transvaginal Ultrasound Scanning – Hazard and Clinical Practice, awarded CCF Grant, 2012). We will arrange Parent Focus Group Meetings alongside their hospital Parent Craft classes so they do not have to devote extra time to this and explore how they feel this research should be conducted. As well as active recruitment, they will also be allowed to self-volunteer to take part in the study with leaflets in various clinical areas. The Imperial Trust website also fosters public interest by including

links to the Clinical Research Network Coordinating Centre, Women's Health Research Centre and to the ongoing various projects.

4.13 Dissemination to participants

Participants, if consented, will be emailed the results of the study in the form of anonymised published posters and papers.

4.14 External peer review

An earlier version of this protocol has been subject to external peer review by the British Medical Association leading to external funding (Helen Lawson Grant, awarded July 2014)

5. Study Outcome Measures

5.1 Primary measures:

1. Assessing feasibility of ultrasound by comparison with digital vaginal examinations:

- *Digital vaginal examination*: cervical dilatation, head station, caput, moulding, head position
- *Ultrasound*:
 - *Transabdominal Ultrasound*: Fetal head position
 - *Transperineal Ultrasound*: Cervical dilatation, head-perineum distance, caput and moulding

2. Acceptability of Transperineal Ultrasound to patients

3. Dataset for predictive model of outcome of labour of Caesarean section due to failure to progress and/or fetal distress

- Time to delivery

- Mode of delivery
- Primary indication for delivery
 - failure to progress
 - suspected fetal compromise

5.2 Secondary measures:

1. Neonatal outcome

- Gender
- Birth-weight
- Apgar Scores at 1 and 5 minutes
- Cord Gases
 - Fetal acidosis defined as arterial pH <7.10 and base excess >12.0mmol/l
- Neonatal unit admission within 24 hours
- Neonatal morbidity

6. Adverse events and reporting procedure

RISK ASSESSMENT - This study will not involve any risk to the participants. There are no predicted risks associated with the additional transabdominal and transperineal ultrasound scan. The scans will be used at the same settings and duration as routine ultrasound. We will be using probe covers and disinfection spray to clean the probe between patients.

The patient will be managed accordingly in concordance with local guidance and follow up arrangements will be made. The patient will still be followed up for the purposes of the study.

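### Fetal acidosis is defined with the sign of base excess reversed, so the rule as written would identify essentially no acidotic neonate

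*Combined protocol and SAP*

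**What the plan says.** Cord gases are listed under "5.2 Secondary measures" as part of neonatal outcome, with one explicit rule beneath them: "Fetal acidosis defined as arterial pH <7.10 and base excess >12.0mmol/l". The outcome list in the section 1 summary carries the same rule with the same sign.

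Neither place has a minus sign, uses the term base deficit, or says that an absolute value is meant. No other section gives a sign convention. Section 7.1 (Statistical and Data Analysis) states no analysis of any neonatal outcome and no derivation for this one.

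Two other statements show how far the definition reaches. The third primary measure in section 5.1 is "Dataset for predictive model of outcome of labour of Caesarean section due to failure to progress and/or fetal distress", which does not use cord gases. The model sample size in section 7 comes from 15 variables, 10 patients per variable and a 25% Caesarean rate: "This equates to 600 patients needed for the study". Acidosis is not an input.

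**The concern.** In metabolic acidosis base is depleted, so base excess is negative; the same finding can be reported as a positive base deficit. The printed rule uses the name base excess with the threshold and direction that belong to base deficit. A base excess above +12 mmol/l is marked metabolic alkalosis. Because the two conditions are joined by and, a neonate would need a pH below 7.10 and that alkalosis at the same time.

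A derivation coded from the protocol would class truly acidotic neonates as non-cases and return an incidence near zero. That could be taken for a reassuring neonatal result when it is only a consequence of the rule.

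Data entry carries a related risk. Section 4.7 expects up to 8 doctors and midwives to be trained, including in data entry, and section 7.1 has measurements entered online. With no stated convention, one person could enter -12 and another 12 for the same cord gas.

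**Working it through.** No figure in the documents depends on this definition, so there is nothing of the plan's own to reproduce. The check is whether the two printed conditions can hold together.

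**Inputs from the documents (sections 1 and 5.2):** pH limit 7.10; base excess (BE) limit 12.0 mmol/l, direction above.

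**Assumptions, not in the documents:** Henderson-Hasselbalch in the form HCO3 = 0.0307 × pCO2 × 10^(pH − 6.1), and three standard base-excess formulas:

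- A: BE = 0.93 × (HCO3 − 24.4 + 14.83 × (pH − 7.4))
- B: BE = HCO3 − 24.8 + 16.2 × (pH − 7.4)
- C: BE = (1 − 0.014 × Hb) × (HCO3 − 24.8 + (1.43 × Hb + 7.7) × (pH − 7.4)), with Hb 16 g/dl assumed

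**Step 1. The rule as printed, at its own limit (pH 7.10, BE +12).** At pH 7.10, 0.0307 × 10^1.0 = 0.307, so pCO2 = HCO3 / 0.307.

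- A: HCO3 = 12/0.93 + 24.4 + 14.83 × 0.3 = 12.90 + 24.4 + 4.45 = 41.8; pCO2 = 136 mmHg (18.1 kPa)
- B: HCO3 = 12 + 24.8 + 16.2 × 0.3 = 41.7; pCO2 = 136 mmHg (18.1 kPa)
- C: HCO3 = 12/0.776 + 24.8 + 30.58 × 0.3 = 15.46 + 24.8 + 9.17 = 49.4; pCO2 = 161 mmHg (21.5 kPa)

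These are minimum values, and the requirement becomes more extreme as pH falls. At pH 7.00, pCO2 must exceed 177 mmHg (A and B) or 215 mmHg (C).

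**Step 2. The same limit with the sign reversed (pH 7.10, BE −12).**

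| Formula | HCO3 (mmol/l) | pCO2 (mmHg) | pCO2 (kPa) |
|---|---|---|---|
| A | 15.9 | 52 | 6.9 |
| B | 17.7 | 58 | 7.7 |
| C | 18.5 | 60 | 8.0 |

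The two conditions are now compatible and describe metabolic acidosis.

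**Step 3. Base excess in a sample at pH 7.10, by pCO2 (formulas A and C).**

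| pCO2 (mmHg) | HCO3 (mmol/l) | BE, A | BE, C |
|---|---|---|---|
| 40 | 12.3 | −15.4 | −16.8 |
| 60 | 18.4 | −9.7 | −12.1 |
| 80 | 24.6 | −4.0 | −7.3 |
| 100 | 30.7 | +1.7 | −2.5 |
| 120 | 36.8 | +7.4 | +2.2 |

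Even at pCO2 120 mmHg the base excess stays below +12. A purely respiratory acidosis (BE 0) at pH 7.10 has a pCO2 of 94 (A), 97 (B) or 111 mmHg (C), and it too falls 12 mmol/l short. To qualify, a sample would have to combine extreme CO2 retention with markedly raised bicarbonate.

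**Step 4. Could a minus sign have been lost in the text?** That would not rescue the rule. Base excess above −12.0 with pH below 7.10 would admit the neonates with the smaller base deficits and exclude those with the largest. Either the direction or the term must change.

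**The case against.** The strongest reply is that the intent is obvious. The outcome is labelled fetal acidosis and paired with pH below 7.10, so a clinician will read 12.0 as a deficit. The harm needs someone to apply the printed direction to signed analyser values. The documents describe no such derivation: section 7.1 says only that data rules will follow those of an earlier multicentre study, and those rules are not shown.

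The damage may also be recoverable. If pH and base excess are stored as values, reclassification is one line of code, and a zero count could be checked against the pH values. The study is observational, caregivers are blinded to the ultrasound findings, and no safety or efficacy conclusion from acidosis incidence is planned. Finally, the bicarbonate and pCO2 figures rest on outside formulas.

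Much of this stands, and it limits the weight of the point. The near-zero incidence is conditional on literal coding; the reassuring reading is a risk, not a certainty; and the formulas are assumptions, which is why ranges are shown. It does not remove the error. A definition has to work as written for whoever codes it, and no other text in the documents would correct this one. That metabolic acidosis fails the second condition follows from the sign alone, whichever formula is used. Recovery is straightforward only if the raw values are kept with a known sign, which the documents do not establish.

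**Conclusion.** The definition is wrong as written in both places. Taken literally, it excludes every neonate with metabolic acidosis. At its own pH limit it can be met only with bicarbonate of at least about 42 to 49 mmol/l and pCO2 of at least about 136 to 161 mmHg, so expected cases are about zero whatever the true incidence.

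The exclusion of metabolic acidosis needs no numerical assumption. The words essentially none, and the ranges, rest on the three assumed formulas and the assumed haemoglobin, because the documents give no cord-gas distribution. The consequence for results depends on the rule being applied to signed values.

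The point should be corrected but does not threaten the study. It affects one secondary outcome. The primary measures, the prediction-model endpoint and the sample sizes of 42, 250, 600 and 700 are unchanged.

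**What to change.** In the section 1 outcome list and in section 5.2, define fetal acidosis as: arterial pH <7.10 and base deficit >12.0 mmol/l (base excess < -12.0 mmol/l). This keeps the sponsor's own two cut-offs and changes only the direction.

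State the sign convention for the cord-gas field in the database, for example that base excess is entered as the signed analyser value. If data have already been entered, check the signs and rederive the outcome from the recorded pH and base excess.

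The cost is one line of wording in two places and a field note. No sample size or power figure changes.
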